6.6 Dose Modification

6.6.1 Enfortumab Vedotin

For all cohorts, dose reduction to 1, 0.75 or 0.5 mg/kg will be allowed depending on the type and severity of toxicity. Subjects requiring a dose reduction may be re-escalated by 1 dose level (i.e., subjects reduced to 0.75 mg/kg may only be re-escalated to 1 mg/kg) provided the toxicity does not require study drug discontinuation and has returned to baseline or \leq grade 1. If the toxicity recurs, re-escalation will not be permitted. Subjects with \geq grade 2 corneal AEs will not be permitted to dose re-escalate.

Dose modification recommendations for enfortumab vedotin associated toxicity are presented in [Table 7] and [Table 8].

Dose interruptions for any enfortumab vedotin associated toxicities are permitted at the discretion of the investigator. Dose interruptions may last up to 8 weeks (2 cycles) for subjects in cohorts 1 to 8 and up to 6 weeks (2 cycles) for subjects in cohort 9. Dose interruptions for subjects who are deriving clinical benefit from treatment may be extended beyond 8 weeks (cohorts 1 to 8) or 6 weeks (cohort 9) after consultation with the medical monitor on a monthly basis, if the subject's toxicity does not otherwise require permanent discontinuation. During dose interruptions, disease assessments must continue to be performed at the protocol-specified frequency and disease status must remain at least SD per RECIST v1.1. If dose interruption is continuous > 6 months, the subject's study treatment will be permanently discontinued.

For all cohorts, if toxicities are present on day 1 of any cycle and enfortumab vedotin cannot be administered, then the start of the cycle may be delayed.

For cohorts 1 to 8, if toxicities are present on days 8 or 15 of any cycle and require the dose to be held > 3 days, then the dose(s) must be eliminated (skipped), rather than delayed. If a subject only receives the day 1 dose and days 8 and 15 doses need to be eliminated (skipped),

then the subject could resume the next cycle as early as day 22 (new day 1), if the toxicity has resolved by that time.

For cohort 9, if the medical monitor and site investigator determine that a dose interruption for enfortumab vedotin is needed, an interruption of all day 1 dose of pembrolizumab must also occur and may last for up to 3 weeks (1 cycle). Dose interruptions for subjects without prior dose reductions and who are responding to treatment may be dose interrupted beyond 3 weeks with approval of the medical monitor, if the subject's toxicity does not otherwise require permanent discontinuation.

If toxicities warranting a dose delay occur after day 1 dosing and are not resolved prior to day 8 dosing (up to day 10), day 8 enfortumab vedotin administration must be skipped rather than delayed. If a subject is dose-reduced due to toxicity that subsequently resolves, the subject may resume treatment at the original dose at the discretion of the medical monitor and site investigator. The day 8 dose of enfortumab vedotin must be given within 4 days of the planned dose (day 8 + 4 days). If the day 8 dose cannot be administered within this timeframe, the dose should be held until day 1 of the next treatment cycle.

Enfortumab vedotin treatment may be interrupted/delayed for other situations such as medical/surgical events or logistical reasons not related to study therapy. If such situations occur, the same dose interruption/delay instructions above will apply. If there is a dose interruption, the schedule for response assessments will not be adjusted and should still be calculated from cycle 1 day 1. The reason for interruption should be documented in the subject's study record. Participants who experience an unacceptable AE that is clearly attributable only to pembrolizumab may continue on enfortumab vedotin monotherapy until a discontinuation criterion is met.

Table 7 Recommended Dose Modifications for Enfortumab Vedotin Associated Hematologic Toxicity*

Grade 1	Grade 2	Grade 3	Grade 4
Continue at same dose level.	Continue at same dose level. For grade 2 thrombocytopenia withhold dose until toxicity is \leq grade 1 or has returned to baseline, then resume treatment at the same dose level.	Withhold dose until toxicity is \leq grade 1 or has returned to baseline, then resume treatment at the same dose level or consider dose reduction by 1 dose level. Transfusions or growth factors may be used as indicated per institutional guidelines.	Withhold dose until toxicity is \leq grade 1 or has returned to baseline, then reduce dose by 1 dose level and resume treatment or discontinue at the discretion of the investigator. Transfusions or growth factors may be used as indicated per institutional guidelines. For anemia, treatment discontinuation should be strongly considered.
*Hematologic toxicity refers to anemia, thrombocytopenia, neutropenia and febrile neutropenia.			

Table 8 Recommended Dose Modifications for Enfortumab Vedotin Associated Non-hematologic Toxicity

Toxicity	Grade			
Skin reactions	Any grade			
	For suspected SJS, suspected TEN or bullous lesions, immediately withhold EV and refer the subject to a dermatologist/specialist for diagnosis and specialized care. For confirmed SJS or TEN, permanently discontinue treatment. If SJS or TEN is ruled out, see recommendations provided below for skin reactions.			
	Grade 1	Grade 2	Grade 3	Grade 4
	Continue at same dose level. For grade 1 rash or skin reactions, the subject may continue at the same dose level. See also [Section 6.6.1.1] for recommended management of rash.	Continue at same dose level. For worsening rash or skin reactions or skin reactions with concomitant fever, withhold enfortumab vedotin until toxicity is \leq grade 1 or has returned to baseline, and then resume treatment at the same dose level or consider dose reduction by 1 level. Consider referral of the subject to a dermatologist/specialist for diagnosis and specialized care.	Withhold enfortumab vedotin until toxicity is \leq grade 1 or has returned to baseline, and then resume treatment at the same dose level or consider dose reduction by 1 level. Consider referral of the subject to a dermatologist/specialist for diagnosis and specialized care. Subjects who have confirmed SJS or recurrent \geq grade 3 rash events should have therapy permanently discontinued.	For grade 4 AEs, discontinue treatment. ² For confirmed SJS or TEN, or grade 4 rash or skin reactions, permanently discontinue treatment.

Toxicity	Grade			
Ocular	Grade 1	Grade 2	Grade 3	Grade 4
	If ocular symptoms and/or changes in vision are identified, the subject should be evaluated with an ophthalmologic exam. ¹	
Withhold dose until toxicity is \leq grade 1 or has returned to baseline, and then resume treatment at the same dose level. For the second occurrence of grade 2 corneal AEs withhold dose until toxicity is \leq grade 1, and then reduce the dose by 1 dose level and resume treatment.
 
If ocular symptoms and/or changes in vision are identified, the subject should be evaluated with an ophthalmologic exam.¹
	
Discontinue treatment at the discretion of the investigator.
 
If ocular symptoms and/or changes in vision are identified, the subject should be evaluated with an ophthalmologic exam.¹
	For grade 4 AEs, discontinue treatment.
Neuropathy	Grade 1	Grade 2	Grade 3	Grade 4
	Continue at same dose level.	Withhold dose until toxicity is \leq grade 1 or has returned to baseline, and then resume treatment at the same dose level. For the second occurrence of grade 2 neuropathy withhold dose until toxicity is \leq grade 1, and then reduce the dose by 1 dose level and resume treatment.	Discontinue treatment at the discretion of the investigator.	For grade 4 AEs, discontinue treatment.

Toxicity	Grade			
	Grade 1	Grade 2	Grade 3	Grade 4
Gastrointestinal	Continue at same dose level.	Continue at same dose level.	Withhold dose until toxicity is \leq grade 1 or has returned to baseline, then resume treatment at the same dose level or consider dose reduction by 1 dose level. ²	For grade 4 AEs, discontinue treatment. grade 4 vomiting and/or diarrhea that improves to \leq grade 2 within 72 hours with supportive management does not require discontinuation.
Hyperglycemia	Continue at same dose level.	Continue at same dose level.	Withhold study treatment. Resume treatment once hyperglycemia/elevated blood glucose has improved to \leq grade 2 and subject is clinically and metabolically stable.	Withhold enfortumab vedotin treatment and undertake a full evaluation of the hyperglycemia to determine the underlying diagnosis. Once blood glucose returns to \leq grade 2, drug dosing may resume with close monitoring after consultation with the medical monitor.

Toxicity	Grade			
Pneumonitis/ILD	Grade 1 Continue at same dose level.	Grade 2 Withhold dose until \leq grade 1, then resume at the same dose level or consider dose reduction by 1 dose level.	Grade 3 Permanently discontinue treatment.	Grade 4 Permanently discontinue treatment.
All Other (not previously mentioned)	Grade 1 Continue at same dose level.	Grade 2 Continue at same dose level.	Grade 3 Withhold dose until toxicity is \leq grade 1 or has returned to baseline, then resume treatment at the same dose level or consider dose reduction by 1 dose level. ³	Grade 4 For grade 4 AEs, discontinue treatment. ³

AEs: adverse events; SJS: Stevens-Johnson Syndrome; TEN: toxic epidermal necrolysis
 
 1. Ophthalmologic exam should be performed by an ophthalmologist. In countries where optometrists can perform exams and prescribe medications, an optometrist may be used instead. 2. Grade 3/4 electrolyte imbalances/laboratory abnormalities that are not associated with clinical sequelae and/or are corrected with supplementation/appropriate management within 72 hours of their onset do not require discontinuation (e.g., grade 4 hyperuricemia). 3. Grade 3 or 4 elevations of amylase or lipase, if asymptomatic do not require treatment delay. 				

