Subjects in cohort 9 who discontinue study treatment (both enfortumab vedotin and pembrolizumab) for reasons other than radiologically confirmed disease progression per iRECIST will enter into a post treatment follow-up period and have physical exams, ECOG and disease assessments every 6 weeks (\pm 7 days) up to 18 months after first dose, then every 9 weeks (\pm 7 days) until the subject has radiologically confirmed disease progression per iRECIST as determined by the investigator, initiates a subsequent anticancer therapy, dies, withdraws consent, or the study closes. During study treatment, palliative radiotherapy on a nontarget lesion that is not progressing will not be considered a subsequent anticancer therapy; however, radiotherapy on any target lesion will be a subsequent anticancer therapy.

Copies of all imaging scans will also be sent to the independent review facility in a timely manner. Images at the independent review facility will be stored. Imaging scans for a cohort may be read at the independent review facility when the minimum number of responders per investigator assessment (subjects with confirmed CR and PR) to claim promising antitumor activity at stage 1 are met based on the 2-stage BOP2 design. Central images may also be read in certain circumstances as determined by the sponsor.

An end of treatment (EOT) visit will be performed within 7 days after the last dose of enfortumab vedotin or the decision to discontinue treatment, or prior to initiation of another

anticancer therapy, whichever occurs earlier. This will be followed by a 30-day safety follow-up to be completed 30 days (+ 7-day window) from the last dose of enfortumab vedotin. The 30-day follow-up assessments should be completed prior to the initiation of another anticancer therapy.

After radiologically-confirmed disease progression or initiation of subsequent anticancer therapy, whichever occurs first, subjects will be contacted every 12 weeks in the long-term follow-up period for survival status until death, withdrawal of consent, lost to follow-up or study closure, whichever occurs first. Telephone contact with the subject is sufficient in the long-term follow-up period unless any assessment must be repeated to confirm resolution of drug-related AEs.

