8 DISCONTINUATION

8.1 Discontinuation of Individual Subject(s) From Study Treatment

A discontinuation from treatment is defined as a subject who enrolled in the study and for whom study treatment is permanently discontinued for any reason.

The subject is free to withdraw from the study treatment and/or study for any reason and at any time without giving reason for doing so and without penalty or prejudice. The investigator is also free to discontinue the subject from study treatment or to terminate a subject's involvement in the study at any time if the subject's clinical condition warrants it.

The reason for discontinuation from study treatment must be documented in the subject's medical records.

A subject must discontinue study treatment for any of the following reasons:

- Subject develops documented radiological disease progression (iCPD per iRECIST) in cohort 9).
- Subject starts a new anticancer therapy.
- Subject develops unacceptable toxicity.
- Female subject becomes pregnant.
- Investigator decides it is in the subject's best interest to discontinue.
- Subject requests to stop treatment.
- Subject is noncompliant with the protocol based on the investigator or medical monitor assessment.
- Subject has continuous dose interruption > 6 months.
- Study is terminated by sponsor.

For subjects in cohort 9, Pembrolizumab may be administered for up to a total of 35 cycles (approximately 2 years). Subjects who experience an unacceptable AE that is clearly attributable only to pembrolizumab may continue on enfortumab vedotin monotherapy until a discontinuation criterion is met. Subjects who experience unacceptable toxicity that is clearly attributable only to enfortumab vedotin may continue on pembrolizumab monotherapy up to a maximum of 35 cycles.

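### Cohort 9 rules in the protocol do not agree on re-escalation, the last-dose anchor for follow-up visits, interruption conditions and a late day 8 dose

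*Protocol*

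**What the plan says.** Four groups of passages bear on cohort 9 (EV is enfortumab vedotin).

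- **Re-escalation.** Protocol 6.6.1 opens with a rule for every cohort: after a reduction the dose may rise by one level, so that "subjects reduced to 0.75 mg/kg may only be re-escalated to 1 mg/kg", and it may not rise at all after a corneal event of grade 2 or higher. Lower in the section, in the cohort 9 block, once the toxicity has resolved "the subject may resume treatment at the original dose at the discretion of the medical monitor and site investigator". Neither limit is repeated there.
- **Last-dose anchor.** Protocol 4.1 and SAP 2.2 place the end-of-treatment (EOT) visit within 7 days of the last EV dose and set a "30-day safety follow-up to be completed 30 days (+ 7-day window) from the last dose of enfortumab vedotin". Table 2 footnote 21 anchors EOT the same way. Protocol 8.1 lets subjects whose toxicity is due only to EV stay on the other drug: they "may continue on pembrolizumab monotherapy up to a maximum of 35 cycles" (6.6.2.1 agrees). Protocol 4.1 treats cohort 9 study treatment as discontinued only when both drugs have stopped.
- **Interruption.** The general text of 6.6.1, and the synopsis, let EV be interrupted for "up to 6 weeks (2 cycles) for subjects in cohort 9". For subjects with clinical benefit this "may be extended beyond 8 weeks (cohorts 1 to 8) or 6 weeks (cohort 9) after consultation with the medical monitor on a monthly basis". The cohort 9 block then says that with an EV interruption "an interruption of all day 1 dose of pembrolizumab must also occur and may last for up to 3 weeks (1 cycle". Its next sentence lets dose interruptions pass 3 weeks only for responding subjects with no prior reduction and with medical monitor approval.
- **Day 8.** The cohort 9 block says that if toxicity has not resolved by day 10 the day 8 dose is skipped, not delayed. Two sentences later: "The day 8 dose of enfortumab vedotin must be given within 4 days of the planned dose (day 8 + 4 days".

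**The concern.** These are operative instructions. A site can comply with one sentence and breach another, and two sites can treat the same situation differently while each cites the protocol.

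On re-escalation, the conflict reaches deviation coding. PD3 (Protocol 10.3, SAP 6.2.2) flags an EV dose more than 10% from the intended dose, and the two texts can imply different intended doses. On the anchor, the EOT and 30-day safety visits are meant to describe the subject at and after the end of treatment. Under the current text they can take place while pembrolizumab is still being given. A subject could then be counted as having completed 30-day safety follow-up (SAP 6.2.1) while still on treatment.

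**Working it through.** No sample-size, power or error-rate figure is involved, so there is no plan figure to reproduce. The check sets the passages side by side and does dose-level and calendar arithmetic.

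**1. Re-escalation.** Inputs: starting dose 1.25 mg/kg with reductions to 1, 0.75 or 0.5 mg/kg (Protocol 6.6.1); PD3 limits of 90% and 110% of the intended dose (SAP 6.2.2). Ratio = original dose / dose under the general rule.

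| Reduced to (mg/kg) | General rule | Original-dose sentence | Difference | Ratio |
|---|---|---|---|---|
| 1.0 (one reduction) | 1.25 | 1.25 | 0 | 100% |
| 0.75 (two) | 1.0 | 1.25 | 0.25 | 125% |
| 0.5 (three) | 0.75 | 1.25 | 0.50 | 167% |
| 1.0, after a corneal event of grade 2 or higher | 1.0 (barred) | 1.25 | 0.25 | 125% |

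After a single reduction with no corneal bar, the texts agree. In the other rows the ratio exceeds 110%, so if the general rule fixes the intended dose, a dose allowed by the cohort 9 sentence is a PD3 deviation.

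**2. Last-dose anchor.** Cycles last 21 days, so day 1 of cycle k is study day 1 + 21(k − 1), and cycle 35 starts on day 1 + 21 × 34 = 715.

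- Last EV dose on cycle 1 day 8: EOT is due by day 8 + 7 = 15, and the safety visit on days 38 to 45. Pembrolizumab could run to day 715.
- Last EV dose on day 1 of cycle 6: cycle 35 starts 29 × 21 = 609 days later, and 609 / 30.4375 = 20.0 months.
- These are extremes, but little is needed to produce the problem. On schedule, the next pembrolizumab dose comes 21 days after a day 1 EV dose, or 14 days after a day 8 dose. Both lie beyond the 7-day EOT limit, so one pembrolizumab-only dose is enough to put EOT before the last dose. After a day 1 EV dose, the second such dose (42 days) already falls after the safety-visit window (30 to 37 days).

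The EOT text also takes the earliest of its triggers, so a later decision to stop pembrolizumab does not move the visit.

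The adverse event text uses a different anchor. Table 2 footnote 9 collects events to 30 days after the last dose of study treatment, and SAP 5.4 counts serious events in cohort 9 to 90 days after the last dose of either drug.

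**3. Interruption.** One cycle is 21 days (3 weeks) and two are 42 days (6 weeks), so each figure is right in itself. Take a subject with stable disease and one prior reduction whose EV is held for 5 weeks. Under the general rule this is inside 6 weeks and needs no extension. Under the cohort 9 block it is past 3 weeks, and the extension is closed on two counts: the subject is not responding and has had a reduction.

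**4. Day 8.** The window ends on day 8 + 4 = 12, and the toxicity cut-off is day 10. Toxicity resolving on day 11 or 12 is therefore a skipped dose under one sentence and inside the window under the other. Table 2 adds a third version: its day 8 visit window ends on day 11 in cycles 1 and 2 (8 + 3) and on day 12 later (8 + 4).

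**The case against.** A fair defence narrows the point in several places.

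- **Interruption.** A reader might infer a flat contradiction of 3 against 6 weeks for EV. The grammar does not support that: the 3 weeks attaches to the pembrolizumab interruption, and both limits can be extended through the medical monitor. What stands is the coupling of the two drugs, together with a following sentence, in the EV section, that applies a 3-week threshold to dose interruptions on different conditions.
- **Day 8.** Day 10 can be read as a toxicity rule inside a wider administration window. That works except for toxicity resolving on day 11 or 12.
- **Anchor.** This is an EV-only anchor that does not fit the two-drug rules, not two competing numbers. The Table 2 column headings name no drug, although footnote 21 does for EOT. A reader might infer that adverse events after EV stops go unrecorded. They do not: collection follows study treatment, deaths are reported to 90 days after the last pembrolizumab dose (Protocol 7.3.5), and subjects on pembrolizumab alone still attend on day 1 of each cycle.
- **Deviations and exposure.** A reader might infer that passing 3 or 6 weeks triggers PD2. It does not, because the withdrawal criterion is a continuous interruption of more than 6 months (Protocol 8.1). Nor do the exposure derivations change: SAP 5.5.2 computes dose intensity from the drug administered and the initial dose, whichever paragraph the site followed.

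**Conclusion.** The inconsistency is real and specific to cohort 9. The two firm strands are re-escalation and the last-dose anchor. The re-escalation texts differ by 0.25 mg/kg after two reductions, by 0.50 mg/kg after three, and also wherever the corneal bar applies. The EOT visit precedes the last dose in any subject who receives even one scheduled pembrolizumab-only dose after EV stops, and this text ties neither visit to the last pembrolizumab dose. The interruption strand is a conflict of coupling and extension conditions. The day 8 strand concerns toxicity resolving on day 11 or 12 only.

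The conclusion rests on three assumptions: that the original-dose sentence belongs to the cohort 9 block, as its position beside the day 8 rules indicates; that PD3 would be judged against the general re-escalation rule; and, for the calendar examples, that cycles run on schedule. How many subjects would be affected cannot be derived from the documents.

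A reader might infer an effect on the primary result. None is shown: the confirmed response definition uses none of these rules, and response scans stay timed from cycle 1 day 1 during interruptions (Protocol 6.6.1).

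**What to change.** Reconcile the passages for cohort 9, with the sponsor's clinical team choosing each rule:

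- **Interruption and re-escalation:** the synopsis dosing text for both drugs, the general and cohort 9 parts of Protocol 6.6.1, and 6.6.2.3. State how the two drugs' limits and extension conditions relate, and whether the one-level limit and corneal bar apply to cohort 9. Say which text fixes the intended dose for PD3 in Protocol 10.3 and SAP 6.2.2.
- **Day 8:** the two sentences in 6.6.1 and the Table 2 windows.
- **Last-dose anchor:** Protocol 4.1, Table 2 footnote 21 and SAP 2.2, read with Table 2 footnote 9, Protocol 8.1 and SAP 5.4. State which last dose anchors the EOT and 30-day visits when one drug continues alone, and use it in the SAP 6.2.1 follow-up summary.

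The cost is a protocol clarification, a site memo and matching SAP wording. The sample size, decision boundaries and efficacy analyses do not change.

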4.2 Dose Rationale

4.2.1 Enfortumab Vedotin

In cohorts 1 to 8, subjects will receive enfortumab vedotin at a dose of 1.25 mg/kg as an intravenous infusion on days 1, 8 and 15 of each 28-day cycle. This dose and regimen has demonstrated an acceptable safety profile and encouraging clinical activity in the phase 1 study (EV-101 [ASG-22CE-13-2]), the phase 2 study (EV-201) and the phase 3 study (EV-301).

The phase 1 study (EV-101) evaluated escalating dose levels of 0.5, 0.75, 1 and 1.25 mg/kg, with expansion cohorts at the 0.75, 1, and 1.25 mg/kg dose levels. A maximum tolerated dose (MTD) was not reached in this study. At the 1 mg/kg dose level, 2 dose-limiting toxicities (DLTs) were observed: grade 3 proctalgia (later changed to grade 2 by the investigator) thought related to radiation recall and grade 4 hyperuricemia without clinical sequelae. No DLT was observed at 1.25 mg/kg and doses above 1.25 mg/kg were not tested.

EV-201 is a single-arm study of enfortumab vedotin (1.25 mg/kg intravenously on days 1, 8, and 15 of every 28-day cycle) in subjects with urothelial carcinoma from the US and Japan. Results from this study were consistent with the EV-101 study. AEs in cohort 1 (n = 125) were consistent with those previously reported in enfortumab vedotin clinical development program.

EV-301 (7465-CL-0301) is a phase 3 study evaluating the safety and efficacy of enfortumab vedotin given as monotherapy on days 1, 8 and 15 of each 28-day cycle versus chemotherapy

in subjects with locally advanced or metastatic UC who were previously treated with chemotherapy and PD-1/PD-L1 inhibitors. The observed safety and efficacy results of EV-301 further support the 1.25 mg/kg dose regimen.

Incidence of some of the most frequent drug-related AEs, such as diarrhea and rash, although primarily grades 1 to 2 and clinically manageable, increased with increasing dose levels. Moreover, dose reductions due to AEs were more frequent for the 1.25 mg/kg vs lower dose levels. Safety assessments of both metastatic urothelial cancer subjects and nonmetastatic urothelial cancer subjects showed that frequency of all TEAEs, AEs leading to withdrawal, and grade 3 to 4 TEAEs were comparable across all dose levels.

While all doses of enfortumab vedotin demonstrated activity, the 1.25 mg/kg dose was associated with the highest activity and had an acceptable safety profile.

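### Protocol Table 8 gives two conflicting instructions for grade 4 laboratory-only events: the 'All Other' row says discontinue, while footnote 2 says discontinuation is not required

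*Protocol*

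**What the plan says.** Protocol Section 6.6.1, Table 8, lists toxicities by row: skin reactions, ocular, neuropathy, gastrointestinal, hyperglycemia, pneumonitis/ILD, and a residual row, 'All Other'. Three numbered footnotes follow.

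- Footnote 2 concerns "Grade 3/4 electrolyte imbalances/laboratory abnormalities that are not associated with clinical sequelae and/or are corrected with supplementation/appropriate management within 72 hours of their onset". It says that these "do not require discontinuation (e.g., grade 4 hyperuricemia").
- Footnote 3 concerns only amylase and lipase elevations without symptoms, and waives treatment delay. It does not mention discontinuation.
- The skin reactions grade 4 cell reads "For grade 4 AEs, discontinue treatment. ² For confirmed SJS or TEN, or grade 4 rash or skin reactions, permanently discontinue treatment".
- The gastrointestinal grade 3 cell says to withhold until recovery, "then resume treatment at the same dose level or consider dose reduction by 1 dose level. ²".
- The 'All Other' grade 3 cell says the same but points to the other footnote: "then resume treatment at the same dose level or consider dose reduction by 1 dose level. ³".
- The 'All Other' grade 4 cell reads "For grade 4 AEs, discontinue treatment. ³".

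Protocol Section 8.1 defines discontinuation from treatment as permanent. SAP Section 6.5.1 tabulates TEAEs leading to permanent discontinuation by cohort and overall, and separately for those judged drug-related.

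**The concern.** A footnote marker tells the reader which cell the exception modifies. The exception for laboratory-only events is marked on two cells that do not deal with laboratory events. It is not marked on the one cell that both covers them and calls for stopping. A site that works from the row reaches one action for grade 4 hyperuricemia, and a site that works from the footnote text reaches the opposite one.

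Two things are at stake. For a subject, it is whether enfortumab vedotin is permanently stopped for a laboratory value that had no clinical consequence or was quickly corrected. For the analysis, the count of TEAEs leading to permanent discontinuation would partly reflect how each site reads the table. A further, smaller question is whether a site that continued treatment under footnote 2 has a PD2 deviation (withdrawal criteria met but subject not withdrawn) under Protocol Section 10.3.

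**Working it through.** There is no planned figure to reproduce. The check is to trace each marker to its cell and then follow the table for the footnote's own example.

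**Step 1. Where the markers sit.**

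| Cell in Table 8 | Action in the cell | Marker | Can that footnote act there? |
|---|---|---|---|
| Skin reactions, grade 4 | Discontinue | 2 | No: a skin reaction is not a laboratory abnormality |
| Gastrointestinal, grade 3 | Withhold, then resume | 2 | No: the cell does not call for discontinuation |
| Gastrointestinal, grade 4 | Discontinue, with its own 72-hour exception for vomiting and diarrhea | none | n/a |
| All Other, grade 3 | Withhold, then resume | 3 | Only for asymptomatic amylase or lipase |
| All Other, grade 4 | Discontinue | 3 | Only for asymptomatic amylase or lipase, and only as to delay |

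Marker 2 therefore occurs twice, and not at all in 'All Other'. Marker 3 occurs twice, both times in 'All Other'.

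**Step 2. Which row holds the example.** Hyperuricemia fits none of the six named rows, so it goes to 'All Other'. So do most other electrolyte and laboratory events. The exceptions are glucose, which has its own row, and the hematologic toxicities, which are in Table 7.

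**Step 3. Follow both routes for grade 4 hyperuricemia without sequelae.**

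- By the row: 'All Other', grade 4, gives discontinue. The only marker leads to footnote 3, which does not cover uric acid.
- By the footnote: footnote 2 names this event and says that discontinuation is not required.

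The two routes give opposite answers. The conflict is confined to grade 4. At grade 3 the 'All Other' cell does not ask for discontinuation, so footnote 2 does not contradict it.

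**Step 4. Can the event be reached?** Uric acid, potassium, sodium, magnesium, phosphate and corrected calcium are in the biochemistry panel (Protocol Appendix 12.7), which is scheduled repeatedly on treatment (Tables 1 and 2). Protocol Section 4.2.1 reports "grade 4 hyperuricemia without clinical sequelae" as one of two dose-limiting toxicities at 1 mg/kg in EV-101. The same paragraph reports no dose-limiting toxicity at 1.25 mg/kg, the starting dose here.

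**Step 5. Size.** The documents give no rate of grade 4 laboratory-only events, so no expected count can be derived. Per subject, with 40 in a cohort, the discontinuation percentage moves by 1/40 = 2.5 percentage points.

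**The case against.** The strongest reply is that footnote 2 defines its scope by type of event and not by row, stands directly beneath the 'All Other' row, and names hyperuricemia. Since its example cannot belong where the marker sits, a careful site would apply it to the whole table. This stands in part: a reader might infer that Table 8 simply orders discontinuation for grade 4 hyperuricemia, and it does not. It gives two instructions. A table-wide reading is available but is not what the markers say.

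Second, Table 8 is titled as recommendations, and the mandatory list in Protocol Section 8.1 speaks of unacceptable toxicity and investigator judgement without citing Table 8 grades. This stands and weakens the PD2 question. The grade 4 cell is nevertheless worded as a directive.

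Third, the skin marker might be read as waiving discontinuation for a grade 4 skin reaction. The documents do not support that. Footnote 2 is limited to laboratory abnormalities, and the rest of the cell asks for permanent discontinuation. The marker there, like the one at gastrointestinal grade 3, is inert and not contradictory.

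Fourth, the EV-101 event might be taken to show that such events are frequent. It is a single event at a lower dose level and supports no rate.

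Fifth, a reader might infer that all study treatment ends. In cohort 9, Section 8.1 allows pembrolizumab alone after toxicity clearly attributable only to enfortumab vedotin.

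Finally, superscripts in a table that spans several pages deserve a check against the master document. The placement is consistent, however: marker 1 is on the ocular examination text and marker 3 on both 'All Other' cells.

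**Conclusion.** The point holds as an internal inconsistency. For grade 4 laboratory-only events outside the named rows, Table 8 gives two conflicting instructions, and the event that footnote 2 uses as its example is one of them. This is more than a clerical slip, because the table guides whether a subject stays on enfortumab vedotin and feeds a tabulated safety result.

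The effect is limited. An affected subject needs an event that is associated with enfortumab vedotin, grade 4, laboratory-only, and either without sequelae or corrected within 72 hours, at a site that follows the row over the footnote. The documents give no rate, and the number is probably small. The discontinuation tables are descriptive, with no test attached. The primary endpoint definition, sample size and decision boundaries are unaffected. Subjects who stop for reasons other than progression continue to be imaged (Protocol Section 4.1), so stopping does not by itself end response follow-up.

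The conclusion assumes that the superscripts are placed as printed and that hyperuricemia belongs in the residual row. It takes no position on which clinical instruction is right.

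**What to change.** Reconcile three elements of Table 8: the 'All Other' grade 4 instruction, the placement of the footnote 2 markers, and the footnote 2 example, so that a reader starting from the row and one starting from the footnote reach the same action. Check at the same time whether the markers at skin grade 4 and gastrointestinal grade 3 are intended. The sponsor's medical team decides which instruction stands.

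The cost is a correction to markers or wording in one table and a memo to sites. No analysis in the SAP needs to change. If the discontinuation data already include such events, listing them with the site's stated reason would show whether the conflict had any effect.
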